8.7.2. Dose Modifications for Overlapping Toxicities

For general overlapping toxicities, the following guidance is recommended after ruling out alternative causes:

- If the non-hematological toxicity is attributable to selinexor, please follow the recommended management actions for the respective AE type, outlined in Table 5.
- If the toxicity is attributable to pembrolizumab, please refer to the pembrolizumab product insert for the management of the AE.
- The management of overlapping toxicities should include withholding pembrolizumab and starting corticosteroids until the toxicity is Grade ≤ 1 or at baseline before restarting at the next cycle:
 - The corticosteroid dosing for intolerable Grade 2 or Grade 3 toxicities is 0.5-1 mg/kg/day of prednisone or equivalent with a slow taper until the event is back to Grade ≤ 1 .

- For Grade 4 toxicities or recurrent Grade 3 toxicities, the dose of corticosteroids is 1-2 mg/kg/day of prednisone or equivalent with a slow taper over 3-6 weeks until the event is back to Grade ≤ 1
- If the AE recurs again, stop pembrolizumab permanently

Table 3 summarizes the selinexor dose levels for modification; **Table 4** describes supportive care and dose adjustment guidelines for hematologic adverse reactions. **Table 5** describes dose adjustment guidelines for non-hematologic adverse reactions. Deviations from the guidelines are permitted after discussion between the Sponsor and the treating physician.

Table 3: Selinexor Dose Modification Steps for Adverse Reactions

Recommended Starting Dosage	First Reduction	Second Reduction	Third Reduction	Fourth Reduction
80 mg Once weekly	60 mg Once weekly	40 mg Once weekly	20 mg Once weekly	Discontinue

Table 4: Dose Modification for Hematologic Adverse Reactions

Adverse Reaction	Occurrence	Action
Thrombocytopenia		
Platelet count $< 50,000 \mu\text{L}$ (Grade 3-4)	First Occurrence	Hold selinexor until platelets recover to $\geq 75,000$ Restart selinexor at same dose level (see Table 3). Consider additional supportive care and discuss with Sponsor's Medical Monitor
	2 nd and subsequent	Hold selinexor until platelets recover to $\geq 75,000$ Reduce selinexor by 1 dose level (see Table 3). Consider additional supportive care and discuss with Sponsor's Medical Monitor

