Platelet count $< 50,000 \mu\text{L}$ with concurrent bleeding	Any	Hold selinexor until platelets recover to $\geq 50,000$ and bleeding has resolved. Restart selinexor at 1 lower dose level (see Table 3) Consider additional supportive care and discuss with Sponsor's Medical Monitor
Neutropenia		
Absolute neutrophil count (ANC) of 0.5 to $1.0 \times 10^9/\text{L}$ (Grade 3)	First Occurrence	Hold selinexor until ANC recover to ≥ 1.0 Restart selinexor at same dose level (see Table 3). Consider additional supportive care and discuss with Sponsor's Medical Monitor

Adverse Reaction	Occurrence	Action
ANC of 0.5 to $1.0 \times 10^9/L$ (Grade 3)	2 nd and subsequent	Hold selinexor until ANC recover to ≥ 1.0 Reduce selinexor by 1 dose level (see Table 3). Consider additional supportive care and discuss with Sponsor's Medical Monitor
ANC $< 0.5 \times 10^9/L$ (Grade 4) OR febrile neutropenia	Any	Hold selinexor until ANC recover to ≥ 1.0 Reduce selinexor by 1 dose level (see Table 3). Consider additional supportive care and discuss with Sponsor's Medical Monitor
Anemia		
Hemoglobin level less than 8.0 g/dL	Any	Administer blood transfusions and/or other treatments per clinical guidelines.
Life-threatening consequences (urgent intervention indicated)	Any	Interrupt selinexor. Monitor hemoglobin until levels return to 8 g/dL or higher. Restart selinexor at 1 dose level lower (see Table 3). Administer blood transfusions and/or other treatments per clinical guidelines.
Overlapping anemia (due to combination of selinexor and pembrolizumab)		Interrupt selinexor Monitor hemoglobin until levels return to ≥ 8 g/dL or baseline Restart selinexor at 1 dose level lower (see Table 3).

^aNational Cancer Institute Common Terminology Criteria for Adverse Events (NCI CTCAE) v5.0.

Table 5: Selinexor Dose Modification Guidelines for Non-hematologic Adverse Reactions

Adverse Reaction ^a	Occurrence	Action
Hyponatremia		
Grade 1 or 2 (sodium level < normal to 130 mmol/L)	Any	Maintain dose Rule out other causes including drug (e.g. diuretic) effects Be certain that reported sodium level is corrected for concurrent hyperglycemia (serum glucose > 150 mg/dL) Treat hyponatremia per institutional guidelines including dietary review Consider addition of salt tablets to patient's diet

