Grade 3 (sodium levels 120 to 129 mmol/L) without symptoms	Any	Rule out other causes including drug (e.g., diuretic) effects Be certain that reported sodium level is corrected for concurrent hyperglycemia (serum glucose > 150mg/dL) If (corrected) sodium is Grade \leq 3 and continues to be asymptomatic, then patient may continue current dosing provided that IV saline and/or salt tablets are provided
Grade 3 (sodium levels 120 to 129 mmol/L) with symptoms OR Grade 4 (sodium levels < 120 mmol/L)	Any	Rule out other causes including drug (e.g., diuretic) effects Be certain that reported sodium level is corrected for concurrent hyperglycemia (serum glucose > 150 mg/dL) Interrupt selinexor dosing until resolved to Grade 1 or baseline and without symptoms. Reduce selinexor by 1 dose level
Overlapping hyponatremia Grade 3 or 4 (due to combination of selinexor and pembrolizumab)	Any	Rule out other causes Interrupt selinexor dosing until resolved to Grade 1 or baseline and without symptoms Restart selinexor at 1 dose level lower (see Table 3).
Fatigue		
Grade 2 lasting greater than 7 days OR Grade 3	Any	Interrupt selinexor. Monitor until fatigue resolves to Grade 1 or baseline. Restart selinexor at 1 dose level lower (see Table 3).
Overlapping fatigue (due to combination of selinexor and pembrolizumab)	Any	Interrupt selinexor. Monitor until fatigue resolves to Grade 1 or baseline. Restart selinexor at 1 dose level lower (see Table 3).
Nausea and Vomiting		

Adverse Reaction ^a	Occurrence	Action
Grade 1 or 2 nausea (oral intake decreased without significant weight loss, dehydration or malnutrition) OR Grade 1 or 2 vomiting (5 or fewer episodes per day)	Any	Maintain selinexor and initiate additional anti-nausea medications.

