Weight loss of 10% to less than 20% OR anorexia associated with significant weight loss or malnutrition	Any	Interrupt selinexor and institute supportive care. Monitor until weight returns to more than 90% of baseline weight. Restart selinexor at 1 dose level lower (see Table 3).
Overlapping anorexia associated with significant weight loss or malnutrition due to combination of selinexor and pembrolizumab	Any	Interrupt selinexor and institute supportive care. Monitor until weight returns to more than 90% of baseline weight. Restart selinexor at 1 dose level lower (see Table 3).
Other Non-Hematologic Adverse Reactions		
Grade 3 or 4	Any	Interrupt selinexor. Monitor until resolved to Grade 2 or lower, restart selinexor at 1 dose level lower (see Table 3).
^a National Cancer Institute Common Terminology Criteria for Adverse Events (NCI CTCAE) v5.0.		

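### Table 5 holds selinexor for anorexia with malnutrition at any weight but states a release on weight alone, so below 10% weight loss no stated release requires the event to improve

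*Protocol*

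**What the plan says.** Table 5 in Protocol 8.7.2 has two rows under Weight Loss and Anorexia.

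- **First row.** It has two alternative triggers: weight loss of 10% to under 20%, or "anorexia associated with significant weight loss or malnutrition".
- **Second row.** It repeats the anorexia trigger for events attributed to both drugs.

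Both rows give the same action. Selinexor is interrupted, supportive care is started, and the instruction is "Monitor until weight returns to more than 90% of baseline weight". Selinexor then restarts one dose level lower. Neither row gives a condition on the anorexia, the nutritional state or the grade.

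Other rows of the same table state the release in terms of the event itself:

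- Fatigue: "Monitor until fatigue resolves to Grade 1 or baseline".
- Hyponatremia, symptomatic Grade 3 or any Grade 4: "Interrupt selinexor dosing until resolved to Grade 1 or baseline and without symptoms".
- Other non-hematologic reactions, Grade 3 or 4: "Monitor until resolved to Grade 2 or lower, restart selinexor at 1 dose level lower".

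The text above the tables also has a general rule for overlapping toxicities: "The management of overlapping toxicities should include withholding pembrolizumab and starting corticosteroids until the toxicity is Grade" 1 or lower, or at baseline, before restarting at the next cycle. That rule concerns pembrolizumab and corticosteroids.

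**The concern.** A hold rule needs a release that matches its trigger. Here one release serves two triggers and matches only the first. A patient can be held for anorexia with malnutrition after losing little weight. For that patient the table does not say what has to get better before selinexor resumes.

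What is at stake is patient safety and consistency of dosing. The event that caused the hold may be unresolved when the drug is given again, and up to 20 sites may handle the same hold in different ways. The setting is foreseeable: Protocol 4.5 names decreased appetite among the potential overlapping toxicities and refers to the dose modifications in Table 5.

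**Working it through.** **1. Does the weight condition bind?** For a loss of L% from baseline, current weight is (100 − L)% of baseline. The release needs more than 90%, so it is already satisfied whenever L is below 10. For illustration, take a baseline of 80 kg (assumed). The release weight is 0.90 × 80 = 72 kg.

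| Weight loss | Current weight | Above 72 kg? |
|---|---|---|
| 3% | 77.6 kg | yes |
| 5% | 76.0 kg | yes |
| 7.5% | 74.0 kg | yes |
| 9.9% | 72.08 kg | yes |
| 10% | 72.0 kg | no |
| 19.9% | 64.08 kg | no |

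The answer depends only on the percentage, so it is the same at any baseline weight. The condition works for the 10% to under 20% trigger and does nothing below it.

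**2. Can a hold start below 10% loss?** Yes. The anorexia trigger is joined to the weight trigger by *or* and carries no percentage. Within it, malnutrition is an alternative to significant weight loss. The Grade 1 or 2 nausea row also lists the two as separate items, so weight does not stand in for malnutrition. Significant weight loss is not defined. If it is read as 10% or more (assumption), only the malnutrition branch is exposed. If it is read as 5% or more (assumption), holds for losses of 5% to under 10% are exposed too. The point needs only the malnutrition branch.

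**3. How do the other Table 5 rows release selinexor?** Counting the rows that interrupt it:

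| Event | Rows | Release stated on |
|---|---|---|
| Hyponatremia | 2 | the event (grade and symptoms) |
| Fatigue | 2 | the event |
| Nausea and vomiting | 2 | the event |
| Diarrhea | 2 | the event |
| Other Grade 3 or 4 | 1 | the event |
| Weight loss and anorexia | 2 | weight only |

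That is 2 + 2 + 2 + 2 + 1 = 9 rows released on recovery of the event and 2 released on weight, 11 in all.

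**4. Does another clause supply the missing release?**

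- The row for other reactions does not apply, because anorexia has its own rows.
- The general overlapping-toxicity rule governs pembrolizumab, not selinexor.
- The 28-day rule (8.7.1) limits long delays. It sets no condition on an earlier restart.
- Skipping a dose (8.7.4), removing a patient from treatment (9.1), discussing immediate safety concerns with the medical monitor (10) and agreeing deviations with the sponsor (8.7.2) are all discretionary. None is a restart criterion.

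**The case against.** **The verb *returns*.** It presupposes that weight has fallen to 90% or below. For a patient who never fell that far, the natural reading is that the weight test does not apply and restart is left to the investigator. An interruption that lapses the moment it is ordered would make no sense. This stands. A reader might infer that the protocol authorises an immediate restart despite malnutrition, but the wording equally supports a release that is simply unspecified for this branch. On both readings nothing stated requires the event to improve, and that is all the point claims.

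**Objective release measures are used elsewhere.** Table 4 releases febrile neutropenia on the neutrophil count ("Hold selinexor until ANC recover to" at least 1.0) and life-threatening anemia on hemoglobin ("Monitor hemoglobin until levels return to 8 g/dL or higher"). So it would be wrong to infer that the protocol always requires the clinical event to recover; the contrast holds within Table 5 only. Weight is scheduled and objective, and it is a reasonable measure to keep. The trouble is that it is the sole criterion for a trigger that does not depend on it.

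**Safeguards.** The tables are guidelines. Supportive care is required, restart is one level lower, nutritional care continues as needed (8.6), and AEs are followed to resolution or until judged permanent (11.1.2). Protocol 4.5 adds close monitoring on Days 1, 15 and 29 of Cycles 1 and 2. In the overlapping row, recovery to Grade 1 or lower or baseline is already required before pembrolizumab restarts. All of this limits the harm, but none of it states a release for selinexor.

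**Rarity.** In the colorectal study of selinexor 80 mg weekly with pembrolizumab (4.4), none of the first 12 patients had a dose reduction, and the one interruption was for nausea. That is 0 of 12 interruptions for anorexia, with an exact two-sided 95% upper limit of 1 − 0.025^(1/12) = 26.5%. Median treatment was only 2.5 cycles of 21 days, and the tumor differs. The data point towards few cases without excluding them.

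**Conclusion.** The point holds as a minor gap in the dose-modification guidance. For selinexor holds due to anorexia with malnutrition and under 10% weight loss, the stated release is already met or does not apply, and no other stated selinexor release requires the triggering event to improve. This follows from the text and rests on no assumption about how *significant* is read.

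The number of patients exposed is unknown and probably small. A reader might try to size it from the 27% with treatment-related decreased appetite on 80 mg weekly in the glioblastoma study (4.4). The documents do not support that. The figure comes from selinexor studied in another tumor and gives no grade. It does not count malnutrition, holds, or weight loss under 10%.

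Nor is there a consequence for the primary result: ORR, its analysis population and the planned analyses in the SAP are unchanged.

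**What to change.** In both rows, replace the release with: *Monitor until weight is more than 90% of baseline weight and the anorexia is no longer associated with significant weight loss or malnutrition, or has returned to baseline.* The return to baseline refers to the anorexia; the weight criterion applies throughout.

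Because the added clause negates the trigger, it is not met at the moment the hold begins. A release at Grade 2 or lower could be, since the trigger carries no grade. Nor would a one-grade improvement be enough, since a fall from Grade 4 to Grade 3 could still carry malnutrition. The sponsor's clinicians may prefer a stricter level, such as the Grade 1 or baseline used for fatigue. Malnutrition and significant weight loss would still be matters of clinical judgement, as they already are for starting the hold.

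The cost is one cell in each of two rows at the next amendment. Some holds will last longer. If a delay for drug-related toxicity passes 28 days (28 / 7 = 4 weekly doses), Protocol 8.7.1 takes the patient off study treatment unless the investigator, with the medical monitor, judges it safe to resume.

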8.7.3. Pembrolizumab Dose Modifications

For AEs related to pembrolizumab, refer to dose adjustment guidelines in the respective drug's prescribing information. If an AE requires interruption of pembrolizumab but not selinexor, selinexor treatment may continue.

Pembrolizumab dosing will be done on D1 of any given 21-day cycle. If an AE requires interruption of only pembrolizumab, but the AE does not require interruption of selinexor, then

pembrolizumab, may remain interrupted as long as is necessary to allow the patient to recover from the AE that caused the drug interruption. If it is determined that the patient should no longer receive pembrolizumab, the patient may continue treatment with single agent selinexor, at the discretion of the Investigator.

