The preclinical and preliminary clinical data of selinexor alone and in combination with pembrolizumab indicates anti-melanoma activity and tolerability that warrant further exploration. Based on the clinical activity and the patients' tolerability seen in the clinical study KCP-330-027

[figure not shown]
mentioned above, the regimen of selinexor 80 mg QW in combination with pembrolizumab will be explored in this study. In this study, we will be using the once every six weeks (Q6W) schedule of pembrolizumab due to the approved use of the 400 mg IV dosing schedule in the US. This open label Phase 2 study is aimed to evaluate the efficacy and safety of selinexor in combination with pembrolizumab in patients with unresectable locally advanced or metastatic (Stage III or IV) melanoma that demonstrated either primary resistance to anti-PD-1/L1 mAb or acquired resistance to anti-PD-1/L1 mAb.

Overall Study Design:

Approximately 40 patients with locally advanced or metastatic melanoma will be enrolled into one of the following 2 arms:

- **Primary resistance to initial checkpoint inhibitor (CPI) therapy (Arm A):** Selinexor 80 mg orally (PO) QW+ Pembrolizumab 400 mg IV Q6W
- **Acquired resistance to initial CPI therapy (Arm B):** Selinexor 80 mg PO QW + Pembrolizumab 400 mg IV Q6W

XPORT-MEL-033 Study Design

CPI: checkpoint inhibitor; Q6W: once every six weeks; QW: once weekly

Objectives and Endpoints: The primary efficacy endpoint for this signal finding study will be ORR assessed using Response Evaluation Criteria in Solid Tumors (RECIST) v1.1 response criteria. Evaluation of the radiographic data for disease progression will be based on a scan review by the Investigator.

The objectives and endpoints for both arms to evaluate the treatment with selinexor plus pembrolizumab are the same and are listed below:

Objectives	Endpoints
Primary	

• To evaluate objective response rate (ORR) per RECIST v1.1 response criteria	
• ORR defined as proportion of patients who achieved a complete response (CR) or partial response (PR).

Secondary	

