3.2. Schedule of Assessments

Table 1: Schedule of Assessments for Study XPORT-MEL-033 (42-Day Cycle)

Activity/Assessment	Screening ^a D -28 to -1	Cycles* 1			Cycles* ≥ 2			EoT Visit ≤ 28 Days Post-Treatment Discontinuation	Follow-up Visit ^b	
		D1	D3±2D	D15/D29 ±3D	D1	D3±2D	D15/D29 ±3D		30 days after EoTVisit +7D	Every 3 months until 12 months ±14D
Procedures										
Informed Consent	X									
Inclusion/Exclusion	X									
Demographics	X									
Medical history	X									
Concomitant Medications Review	X	Continuous					X	X	X	
Prior Melanoma Therapy	X									
Eligibility confirmation by Sponsor ^c	X									
ECOG Daily Living Performance Score	X	X		X						
Nutritional Counselling	X	Throughout, as needed								
Vital signs including weight	X	X		X			X			
Physical Exam – full	X						X		X	
Physical Exam – symptom directed		X		X				X		
Adverse Events ^d		Continuous								
Telephone contact ^e			X					X	X	
Collection of information regarding antineoplastic therapy after EoT								X	X	
Laboratory										
Hematology and Serum Chemistry	X	X		X	X		X	X		

Activity/Assessment	Screening ^a	Cycles* 1			Cycles* ≥2			EoT Visit	Follow-up Visit ^b	
		D -28 to -1	D1	D3±2D	D15/D29 ±3D	D1	D3±2D	D15/D29 ±3D	≤28 Days Post-Treatment Discontinuation	30 days after EoTVisit +7D
LDH	X	X			X			X		
Pregnancy test ^f	X	X						X	X	
CCI										
Drug Administration										
Selinexor		Selinexor will be administered once weekly (Days 1, 8, 15, 22, 29, 36 of 42-day cycle)								
Pembrolizumab		Pembrolizumab will be administered on Day 1 once every 6 weeks								
Anti-tumor Activity										
Tumor assessment by CT or MRI Scan	X	Tumor assessment will be performed every 9 weeks for 6 months, then every 3 months thereafter						X		

CT = computed tomography; D = day; ECOG = Eastern Cooperative Oncology Group; EoT = end of treatment; FU = follow-up; hCG = human chorionic gonadotropin; LDH = lactate dehydrogenase; MRI = magnetic resonance imaging; PDn = pharmacodynamics

* Cycles are 6 weeks in length.

^a Procedures that are performed as part of standard of care should not be repeated if they are within the screening window and are done prior to signing the ICF.

^b After discontinuation of study treatment for reasons other than PD, disease assessments should continue to be performed every 3 months until progression, start of new therapy or withdrawal of consent.

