predominantly nausea, vomiting, diarrhea, fatigue, anorexia and weight loss, and these AEs were assessed as low-grade and manageable with dose modification or supportive care. Hyponatremia (typically asymptomatic), confused state and dizziness have also been reported. On the other hand, hematological AEs including thrombocytopenia, neutropenia and anemia, which can be higher grade, were reported primarily in patients with hematologic malignancies. Any potential overlapping toxicity including fatigue, decreased appetite, diarrhea, nausea, pyrexia, constipation, hyponatremia, and anemia will be monitored closely by careful physical examination and clinical laboratory testing on Days 1, 15, and 29 of Cycles 1 and 2 with dose adjustments as per prespecified dose modifications (see [Table 5](#)). Additional visits to manage AEs and telephone contact are also encouraged based upon the patient's condition.

A summary of the clinical trials, antitumor responses observed, and anticipated AEs of selinexor are found in the Investigator's Brochure.

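### Protocol 8.7.3 ties pembrolizumab to a 21-day cycle, but this trial gives it every 6 weeks in 42-day cycles

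*Protocol*

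**What the plan says.** Section 8.7.3 of the protocol opens by sending sites to the prescribing information ("For AEs related to pembrolizumab, refer to dose adjustment guidelines") and then sets the dosing day: "Pembrolizumab dosing will be done on D1 of any given 21-day cycle". It goes on to allow pembrolizumab to stay on hold for as long as recovery requires.

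The rest of the plan describes a different cycle:

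- Synopsis, study rationale: "we will be using the once every six weeks (Q6W) schedule of pembrolizumab".
- Table 1 (Schedule of Assessments): "Pembrolizumab will be administered on Day 1 once every 6 weeks", with the footnote "Cycles are 6 weeks in length". The selinexor row lists "Days 1, 8, 15, 22, 29, 36 of 42-day cycle".
- Section 4.5 (Benefit/Risk Assessment) describes "clinical laboratory testing on Days 1, 15, and 29 of Cycles 1 and 2".
- The synopsis dosing paragraph, Section 6.1, Table 2 and SAP Section 1.1 all give 400 mg at six-week intervals.
- SAP Section 2.6 puts Day 1 of Cycle 2 on Day 43 and Day 1 of Cycle 3 on Day 85. Its vital-sign windows repeat every 42 days.

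**The concern.** The Section 8.7.3 sentence gives half the cycle length found everywhere else. It is current body text, complete and legible, so neither redaction nor PDF extraction explains the number. It is also worded as an instruction, in the section that a site opens after pembrolizumab has been interrupted.

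Section 8.7.2 makes cycle length matter in that situation. For overlapping toxicities, pembrolizumab is withheld until recovery and resumed with the following cycle. If a cycle is taken to be 21 days, that point can come as early as Day 22; if it is 42 days, it comes no earlier than Day 43. The patients exposed to the ambiguity are those who have just had a toxicity. What is at stake is an infusion given too early, not any endpoint or analysis.

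**Working it through.** The plan has no calculated figure to reproduce here. The check compares every statement of cycle length or pembrolizumab interval and then works out what the literal reading would mean.

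**Step 1: statements side by side**

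| Place | Interval or cycle for this trial |
|---|---|
| Protocol 8.7.3 | 21-day cycle |
| Synopsis, rationale | every 6 weeks |
| Synopsis, dosing | every 6 weeks |
| Table 1, title, footnote and drug rows | 42 days / 6 weeks |
| Section 6.1 | every 6 weeks |
| Table 2 | every 6 weeks |
| SAP 1.1 | every 6 weeks |
| SAP 2.6 | every 42 days |

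Six weeks is 6 × 7 = 42 days, so the seven places other than Section 8.7.3 agree with one another.

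**Step 2: can a 21-day cycle coexist with the schedule?**

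- Table 1 lists six weekly selinexor doses per cycle: 6 × 7 = 42 days. Days 22, 29 and 36 are all greater than 21.
- Section 4.5 refers to laboratory tests on Day 29 of Cycles 1 and 2, and 29 > 21.
- No text sets up a separate 21-day cycle for pembrolizumab alone.
- The only other 21-day cycle in the documents is in Section 4.4. It describes the earlier colorectal study, which gave 200 mg every 3 weeks. Carry-over from a three-weekly regimen is plausible, but that is inference and the finding does not depend on it.

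**Step 3: size under the literal reading**

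- Literal: Day 1, then Day 22; interval 22 − 1 = 21 days.
- Intended: Day 1, then Day 43 (SAP Cycle 2 Day 1); interval 43 − 1 = 42 days.
- Difference: 42 − 21 = 21 days, a factor of 42 / 21 = 2.

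An upper bound assumes that every infusion followed Section 8.7.3 at the 400 mg dose in Table 2:

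- Weekly dose: 400 / 3 = 133.3 mg against 400 / 6 = 66.7 mg.
- Infusions in the first 24 weeks (168 days): 168 / 21 = 8 against 168 / 42 = 4 (Days 1, 43, 85 and 127).

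The modelling cited in Section 4.4 compares 400 mg every 6 weeks with 200 mg every 3 weeks. It does not cover 400 mg every 3 weeks. The upper bound shows the size of the contradiction and does not predict what sites would do.

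**Step 4: after correction**

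With 42 in place of 21, Section 8.7.3 agrees with Tables 1 and 2, Section 6.1, the synopsis and the SAP visit days.

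**The case against.** The strongest case on the other side accepts that the sentence is wrong and disputes how much it matters.

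- Section 8.7.3 gives no dose. A site must look elsewhere for the 400 mg, and the synopsis, Section 6.1 and Table 2 state the six-week interval alongside it. Section 10 makes adherence to the Schedule of Assessments mandatory.
- Table 1 has no clinic visit on Day 22. The neighbouring windows are Days 12 to 18 (Day 15 ± 3) and Days 26 to 32 (Day 29 ± 3). The selinexor dose due on Day 22 is an oral tablet, so an infusion that day would need an unscheduled visit.
- The hold rule in Section 8.7.3 sets no restart interval in days. The instruction to resume with a later cycle is in Section 8.7.2, and Table 1 defines the cycle as six weeks.
- For toxicity attributed to pembrolizumab, Section 8.7.2 says "please refer to the pembrolizumab product insert for the management of the AE", and Section 8.7.3 makes a similar referral.
- Section 4.5 is narrative. It corroborates the laboratory schedule but does not set it.

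All of this stands as evidence that the practical risk is low, and it rules out using the doubled weekly dose to raise the severity. It does not make the sentence right. The label referrals concern managing adverse events and do not correct a cycle length stated for this trial. The label is not among the documents, so how much of the remaining risk it removes cannot be judged here.

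**Conclusion.** The concern holds: Section 8.7.3 is wrong as written. The error is one number, 21 where 42 is meant. Followed literally, it shortens the infusion interval by 21 days and moves the second infusion from Day 43 to Day 22.

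That consequence requires a site to put Section 8.7.3 ahead of Tables 1 and 2 and the visit calendar. The conclusion that 42 is the intended number rests on the agreement of all other statements of this trial's regimen and on scheduled days that cannot exist in a 21-day cycle.

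This is a should-fix point, held with high confidence. The risk is limited, but the number sits in an instruction on giving an intravenous anticancer drug and bears on when treatment resumes after an overlapping toxicity.

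**What to change.** In Protocol Section 8.7.3, replace 21-day cycle with 42-day cycle, and notify sites of the correction. The cost is one number in the protocol and one note to sites, with no change to sample size, the response analysis or the SAP.

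Whether a delayed infusion waits for the next scheduled Day 1 or starts a new cycle is a separate clarification for the sponsor. It is not needed for this correction.
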